"Artificial intelligence to be used as a diagnostic tool in mental health and recommendations for a treatment plan."

As part of this study, we are recruiting men and women over the age of 18. The main purpose of the study is to compare the results of the AI system test with the results of a psychiatrist's examination.

Participation in the study includes arriving at the Sheba Tel Hashomer Hospital for examination by the AI system and a psychiatrist. It will be possible to receive the summary of the meeting with the psychiatrist. Expenses will be reimbursed in the amount of NIS 100.

The details of the subjects will be kept confidential

Those interested in participating are welcome to send a text/WhatsApp message

[contact]

In addition, all participants in the study will be asked to fill out a satisfaction questionnaire (attached Appendix 1). And the examining psychiatrists will be asked to fill out a form of diagnosis, severity and recommendations for drug and psychotherapeutic treatment (attached in Appendix 2). This interview will be audiotape.

The primary outcome of the study will be a comparison of the interviews, differential diagnoses and recommendations for treatment assigned by the AI with those assigned by the board certified psychiatrist. the rates of agreement will be the outcome of interest.

All actors, patients, and psychiatrists participating (The psychiatrists who participate in the actors part) will give informed consent.

security and privacy:

1-Actors in MSR: The interviews will be recorded and stored in the Simboost server managed by MSR.

2-Patients in the Division of Psychiatry and ER: after giving informed consent, the investigators will enter the patients ID number into a conversion table, so that each patient will receive a code number which will identify the patient for AI.

The conversion table and the audiotape interviews will be stored in the Sheba secured server, which be accessed only by the research team.

Statistical Analysis Plan

Data

Actors who simulate one of four psychiatric illnesses (anxiety, depression, PTSD, or Mania) or a control condition that is not considered psychotic) are interviewed by a psychiatrist or a computerized AI program (called Liv), and for each interview the following is recorded:

- (i) Interviewer (psychiatrist or Liv)
- (ii) If psychiatrist, identity number
- (iii) True diagnosis
- (iv) True severity (mild/severe)
- (v) Medication indicated
- (vi) Psychiatric treatment indicated

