- (vii) Primary diagnosis made
- (viii) Secondary and Tertiary diagnoses made
- (ix) Severity (mild/moderate/severe)
- (x) Medications recommended
- (xi) Psychiatric treatment recommended

The codes 0, 5 (no diagnosis) and 9 (adjustment disorder) are taken to be equivalent diagnoses in the analyses described below.

Analyses

Note that in the analyses below, all estimated percentages will be accompanied by a 95% confidence interval.

- (a) Diagnosis:

The overall results will be summarized as:

1. % agreement of the primary diagnosis with gold standard over all conditions: (i) for Liv; (ii) for psychiatrists.
2. % agreement between Liv and psychiatrists; this calculation will need a special method – see paragraph (f) below.
3. The results will be displayed also as cross-tabulations of the 5 conditions according to gold standard versus Liv, according to gold standard versus psychiatrists, and according to psychiatrists versus Liv.
4. Analyses 1, 2, and 3 above will be repeated under the rule that agreement with the gold standard is achieved if one of the diagnoses (primary, secondary or tertiary) agrees with the gold standard, and agreement with the psychiatrists is achieved if one of the Liv diagnoses (primary, secondary or tertiary) agrees with the primary diagnosis of the psychiatrist.

(b) Diagnosis according to severity of condition:

The following analyses will be conducted:

5. As in 1 and 2 above, but for severe conditions only.
6. As in 1 and 2 above, but for mild/moderate conditions only.
7. As in 3 above, but for severe conditions only.
8. As in 3 above, but for mild/moderate conditions only.
9. As in 4 above, but for severe conditions only.
10. As in 4 above, but for mild/moderate conditions only.

(c) Diagnosis and Severity:

Note that throughout, **mild and moderate severity assessments will be considered equivalent**. If the psychiatrist or Liv classifies a patient with mild severity as having moderate severity, this will not be counted as an error.

Severity assessments will be evaluated in two different ways:

First, they will be included as part of the definition of a correct classification: e.g. a patient with severe anxiety will be considered correctly classified only if the psychiatrist or Liv classifies them as having severe anxiety. A classification of mild/moderate anxiety will be counted as an error. Analyses using this type of evaluation are listed below.

11. As in 1 and 2 above.

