12. As in 3 above, but here the table will be a 9 x 9 cross-classification, with the following categories: mild anxiety, severe anxiety, mild depression, severe depression, mild PTSD, severe PTSD, mild Mania, severe Mania, control.

Second, **within the set of correctly assigned primary diagnoses**, we will do the following analyses:

13. % agreement of assigned severity scores with the gold standard (i) for Liv and (ii) for psychiatrists.

14. % agreement of assigned severity scores by Liv versus that assigned by the psychiatrists.

15. The results will be displayed also as 2 x 2 cross-tabulations of the 2 severities according to gold standard versus Liv, according to gold standard versus psychiatrists, and according to psychiatrists versus Liv.

(d) Medications and psychiatric treatments:

Agreement of the recommendations provided by Liv and by the psychiatrists will be compared with the gold standard. As with the second approach to evaluating severity assessments, the comparisons will be made only **within the set of correctly assigned primary diagnoses**.

There will be only one primary gold standard medication (psychiatric treatment), and the recommendation by Liv or the psychiatrist will be judged correct only if it includes this primary medication (psychiatric treatment).

Thus the two main analyses will be:

16. % agreement with primary gold-standard medication of (i) Liv's recommended medication and (ii) psychiatrists' recommended medication.

17. % agreement with primary gold-standard psychiatric treatment of (i) Liv's recommended treatment and (ii) psychiatrists' recommended treatment.

(e) Decision thresholds:

On the basis of certain of the above statistics, we specify two conditions that must be satisfied for Liv to proceed to the Phase II study that involves real patients arriving for diagnosis and treatment at Sheba Medical Center.

A. The % agreement of the psychiatrists' primary diagnosis with the gold standard is >85%.

If it falls below this value, then it will be concluded that the "simulation" was not sufficiently realistic and some adjustments to the training of the actors will need to be made.

B. The % agreement of Liv's primary diagnosis with the psychiatrists' primary diagnosis >85%. If it falls below this value, then it will be concluded that adjustments are required to the Liv program.

Reference

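### Treatment recommendations are scored only after a correct primary diagnosis, so items 16 and 17 never give the all-encounter rate of naming the indicated treatment and compare Liv with psychiatrists on performance-selected encounters

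*Combined protocol and SAP*

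**What the plan says.** In section (d) of the Statistical Analysis Plan, recommendations by Liv and by the psychiatrists are compared with a gold standard. A recommendation is correct if it includes the single primary medication (or psychiatric treatment) set for that case. The set is then restricted: "As with the second approach to evaluating severity assessments, the comparisons will be made only" "within the set of correctly assigned primary diagnoses".

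The two main analyses in (d) are item 16, "agreement with primary gold-standard medication of (i) Liv's recommended medication and (ii) psychiatrists' recommended medication", and item 17, "agreement with primary gold-standard psychiatric treatment of (i) Liv's recommended treatment and (ii) psychiatrists' recommended treatment". Each gives one percentage for Liv and one for the psychiatrists. No treatment percentage over all encounters is listed.

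Severity, in section (c), is handled in two ways. Of the first, the SAP says: "First, they will be included as part of the definition of a correct classification". Under that approach (items 11 and 12) a wrong diagnosis counts as an error. The second approach (items 13 to 15) is limited to correct diagnoses. Section (d) takes over only the second.

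The protocol's Procedure section states: "The primary outcome of the study will be a comparison of the interviews, differential diagnoses and recommendations for treatment assigned by the AI", set against those of the psychiatrist. It does not limit this to correctly diagnosed cases.

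**The concern.** The denominator of items 16 and 17 depends on how well the interviewer diagnosed. An encounter with a missed diagnosis and, as a result, a wrong treatment leaves the treatment analysis instead of counting as a treatment failure. An encounter with a missed primary diagnosis but the indicated treatment also leaves, including one where the true diagnosis was listed second or third, which item 4 accepts as agreement.

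Two things are at stake. First, items 16 and 17 do not say how often an interviewer names the indicated treatment. They say how often it is named once the diagnosis is right. Second, parts (i) and (ii) of each item stand side by side and invite comparison. If Liv and the psychiatrists differ in diagnostic accuracy, the two percentages can look alike when the share of encounters ending in both the right diagnosis and the right treatment is not alike.

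**Working it through.** **Inputs from the documents.** The Procedure section plans 75 AI and 50 psychiatrist encounters with actors: 75 + 50 = 125, which matches the stated total. This is 75/3 = 25 per AI round and 50/2 = 25 per psychiatrist round. No sample size, power or margin is given for the treatment comparison. The SAP attaches a 95% confidence interval to every percentage.

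**Assumed inputs.** The documents give no expected accuracies. Let d be diagnostic accuracy and c the share of correct treatment given a correct diagnosis.

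**Formulas.**
- Items 16 and 17 report c.
- Joint rate (correct diagnosis and correct treatment) = d × c.
- All-encounter rate of naming the indicated treatment lies between d × c, if no dropped encounter includes it, and d × c + (1 − d), if all do.

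**Results with c = 90% for both and psychiatrists at d = 90%.**

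| Liv's d | Items 16/17, Liv v psychiatrists | Joint rate, Liv v psychiatrists | Joint gap | Range of Liv's all-encounter rate |
|---|---|---|---|---|
| 90% | 90% v 90% | 81.0% v 81.0% | 0 | 81.0% to 91.0% |
| 85% | 90% v 90% | 76.5% v 81.0% | 4.5 points | 76.5% to 91.5% |
| 70% | 90% v 90% | 63.0% v 81.0% | 18 points | 63.0% to 93.0% |

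The psychiatrists' all-encounter rate lies between 81.0% and 91.0% in each row.

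**Encounters dropped.** Psychiatrists at 90%: 50 × 0.10 = 5. Liv at 85%: 75 × 0.15 = 11.25, about 11. Liv at 70%: 75 × 0.30 = 22.5.

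**Different encounters.** Treat scenarios as matched and errors as independent. The share that counts for only one interviewer is dL(1 − dP) + dP(1 − dL). At 85% and 90% this is 0.85 × 0.10 + 0.90 × 0.15 = 22%. At 70% and 90% it is 0.70 × 0.10 + 0.90 × 0.30 = 34%.

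**Whole-number check at similar, high accuracy.** Liv 64/75 and psychiatrists 43/50 correct. Conditional: 58/64 = 90.6% v 39/43 = 90.7%. Joint: 58/75 = 77.3% v 39/50 = 78.0%. The contrast hardly changes.

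**What the planned output can recover.** Item 1 × item 16 gives the joint rate, for example 64/75 × 58/64 = 58/75. This is exact when both items use the same encounters. If control cases have no gold-standard medication, accuracy must first be recomputed without them, which the item 3 cross-tabulation allows. The all-encounter rate cannot be recovered, because it needs the recommendations in the dropped encounters.

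**The case against.** The restriction is openly stated, and splitting performance into diagnosis, then treatment given a correct diagnosis, is a legitimate decomposition. Missed diagnoses are not hidden: item 1 counts them as failures, and the joint rate follows by multiplication. This stands. What is lost is the scoring of recommendations after a missed diagnosis, and a treatment contrast that does not depend on each interviewer's own accuracy.

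A reader might infer stronger claims that the documents do not support.

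- *That the rule could carry Liv into Phase II.* Thresholds A and B in section (e) use primary diagnosis only. On matched encounters, Liv-psychiatrist agreement is at most 1 minus the accuracy gap. At 70% v 90% that is 80%, so the 18-point case would fail threshold B. Agreement above 85% keeps the accuracy gap under 15 points and, with c = 90% for both, the joint gap under 0.90 × 15 = 13.5 points.
- *That the weaker diagnostician is scored on easier cases, so the ranking reverses.* This can be constructed. Assume half mild and half severe cases, correct treatment of 70% and 95% for both interviewers, and accuracy of 50%/90% for Liv and 85%/95% for psychiatrists. The conditional figures are then 1.205/1.40 = 86.1% for Liv v 1.4975/1.80 = 83.2%, with joint rates of 60.3% v 74.9%. But that case mix is wholly assumed, and nothing in the documents shows that correctly diagnosed cases are easier to treat. Differences this small would not rank anyone: 41/45 = 91.1% has a Wilson 95% interval of 79.3% to 96.5%, ignoring clustering.
- *That each interviewer's own diagnoses certainly define the set.* The SAP does not say. Separate scoring of (i) and (ii), with one record per interview, points that way. However, item 14 uses the same restriction for Liv-versus-psychiatrist agreement, where both being correct is the easier reading. If (d) meant both correct, the different-encounters part would fall away; the unscored recommendations would remain.
- *That items 16 and 17 misreport the primary outcome.* The primary outcome is AI against psychiatrist, whereas these items compare each with the gold standard, so the link is loose.

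The 75 and 50 encounters also differ before any restriction, because the third round is AI-only and follows technological changes. The fix below does not remove that difference.

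**Conclusion.** The concern holds in a limited form. Section (d) leaves recommendations after a missed diagnosis unscored and, on the natural reading, compares Liv with psychiatrists on performance-selected encounters. The plan's output allows the joint rate to be derived but not the all-encounter rate of naming the indicated treatment.

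With Liv assumed at 85% accuracy, that unrecoverable rate spans 15 points (76.5% to 91.5%), the same as the share of encounters dropped. The hidden joint gap ranges from 0 to 4.5 points for Liv accuracies of 90% to 85%, up to 18 points at 70%. These figures rest on assumed accuracies, on c = 90% for both interviewers, and on reading the set as each interviewer's own correct diagnoses.

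This affects how the treatment results are interpreted, not the decision to proceed. It is worth correcting because the correction is cheap and section (c) already contains the model for it.

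**What to change.** In section (d), add to items 16 and 17, for Liv and for psychiatrists, each with a 95% confidence interval:

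1. the percentage of all encounters having a gold-standard medication (psychiatric treatment) in which the recommendation includes it, whatever diagnosis was assigned;
2. the percentage of those same encounters with both the correct primary diagnosis and the gold-standard medication (psychiatric treatment), which mirrors the first severity approach in (c).

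Both are needed: the first credits an indicated treatment named under a wrong diagnosis, the second does not. Base the Liv-psychiatrist treatment contrast on these figures. Keep the present percentages, labelled as conditional on a correct primary diagnosis, and state whose correct diagnosis defines that set. State also how control cases enter the denominator. If controls are one in five encounters and have no indicated medication (an assumption), the medication denominators are about 75 × 4/5 = 60 and 50 × 4/5 = 40.

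**Cost.** SAP wording and four more percentages per interviewer type (two versions of two items). Indicated and recommended treatments are already recorded in fields (v), (vi), (x) and (xi), and true and assigned diagnoses in (iii) and (vii). The all-encounter treatment figures will probably be lower than the conditional ones.

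### Items 16 and 17 credit a treatment recommendation only if it includes one named item, so they cannot separate unacceptable advice from an acceptable alternative

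*Combined protocol and SAP*

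**What the plan says.** SAP section (d) sets a single reference item for each kind of treatment: "There will be only one primary gold standard medication (psychiatric treatment), and the recommendation by Liv or the psychiatrist will be judged correct only" on one condition. That condition is inclusion: a recommendation "will be judged correct only if it includes this primary medication (psychiatric treatment"). Scoring is restricted to interviews in which the primary diagnosis was right: "As with the second approach to evaluating severity assessments, the comparisons will be made only" in that subset.

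Two percentages follow, which the section presents as its main analyses. Item 16 is "agreement with primary gold-standard medication of (i) Liv's recommended medication and (ii) psychiatrists' recommended medication"; item 17 is "agreement with primary gold-standard psychiatric treatment of (i) Liv's recommended treatment and (ii) psychiatrists' recommended treatment". The SAP plans no other analysis of treatment.

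Other endpoints are given some latitude:

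- Diagnosis codes (SAP, Data): "The codes 0, 5 (no diagnosis) and 9 (adjustment disorder) are taken to be equivalent diagnoses".
- Severity (SAP, section (c)): "mild and moderate severity assessments will be considered equivalent".
- Diagnosis (SAP, item 4): the analyses are repeated with credit for a match on the primary, secondary or tertiary diagnosis.

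The Appendix 2 form gives the psychiatrist four blank medication lines and, for psychotherapy, five named choices plus an open one. The SAP data list records recommended medications in the plural. No limit on Liv's list is stated.

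**The concern.** If the people who set the gold standard would accept more than one medication or psychiatric treatment for a scenario, a recommendation that leaves out the named one is still scored as an error. A low percentage then has two possible causes, unacceptable advice or an acceptable alternative, and the analysis cannot tell them apart. Restricting to correct diagnoses does not help, because the variation in question is in treatment choice within a diagnosis.

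The Liv-psychiatrist contrast has the same weakness. One side may score higher because its preference coincides with the named item, or because it lists more items and so is more likely to include it.

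The protocol's primary outcome covers treatment recommendations as well as diagnoses, and items 16 and 17 are the only place where the SAP analyses them.

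**Working it through.** The documents give no expected rate, sample size or power for items 16 and 17, so there is no planned figure to reproduce. The check compares the rules and then illustrates what the inclusion rule does.

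**1. Rules side by side**

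| Endpoint | Equivalence rule | Lenient repeat |
|---|---|---|
| Diagnosis | codes 0, 5 and 9 merged | yes, item 4 |
| Severity | mild and moderate merged | none |
| Medication (item 16) | none | none |
| Psychiatric treatment (item 17) | none | none |

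**2. Score of a rater who gives only acceptable advice**

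Assumptions, none of them in the documents: k options are equally acceptable, one of them is the named item, and the rater lists m distinct options (m ≤ k) drawn at random from the k.

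P(list includes the named item) = 1 − C(k−1, m)/C(k, m) = 1 − (k−m)/k = m/k.

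| k | m=1 | m=2 | m=3 | m=4 |
|---|---|---|---|---|
| 2 | 50% | 100% | – | – |
| 3 | 33% | 67% | 100% | – |
| 4 | 25% | 50% | 75% | 100% |
| 5 | 20% | 40% | 60% | 80% |

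If any acceptable option counted, every cell would be 100%.

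**3. Effect of list length alone**

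Take k=4 and two raters who both give only acceptable advice. One lists one option and scores 25%; the other lists four and scores 100%. The gap of 100 − 25 = 75 percentage points reflects no difference in acceptability.

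**4. Whether the planned intervals would show it**

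The protocol states 75 AI and 50 psychiatrist encounters in the actors' part. These are upper bounds for the denominators, since only correctly diagnosed interviews are scored. The SAP promises 95% confidence intervals without naming a method; Clopper-Pearson is used here. If all 50 psychiatrist encounters counted:

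- k=2, m=1, single-item rule: 25/50 = 50%, interval 35.5% to 64.5%.
- Any acceptable option counts: 50/50 = 100%, interval 92.9% to 100%.

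The intervals do not overlap. They describe sampling error around whatever the rule measures, so they give no warning that the rule itself lowered the score.

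**The case against.** The strongest reply is that the rule requires inclusion, not an exact match. A reader who stops at the requirement for one gold-standard item might infer that any other item spoils the recommendation. It does not: alternatives may be listed beside the named one, and in the illustration the loss disappears when m=k. This stands, and it is why no single size can be attached to the point. Large artefacts require short lists and several acceptable options, and the documents give neither number.

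A reader might also infer that items 16 and 17 measure prescribing habit and not quality, or that a Liv-psychiatrist gap can come only from shared preference. The documents do not support that. An unsuitable recommendation, or none where medication is indicated, also fails the rule, so real differences in quality move both percentages. What can be said is that quality and preference are mixed.

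The SAP also does not say whether medication means a drug or a class, or who sets the gold standard. A class-level standard would remove much of the problem for item 16, but the SAP would have to state it. No passage shows that an acceptable alternative exists for a given scenario, so the point is conditional on that.

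Finally, both raters face the same rule, and a low psychiatrist score would itself hint that the standard is narrow. That is a useful signal, but it does not identify the cause and does not cover unequal list lengths.

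**Conclusion.** The point holds in a limited form. Section (d) scores as an error any recommendation that omits the single named item, and the SAP has no provision for accepted alternatives. Items 16 and 17 therefore cannot distinguish unacceptable advice from an acceptable alternative, and a Liv-psychiatrist gap may come partly or wholly from preference or list length.

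The size is unknown. Under the stated assumptions, a rater giving only acceptable advice scores m/k: 25% to 50% for k from 2 to 4 with one item listed, rising to 100% when all acceptable options are listed.

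A reader might suppose that the rule could block or release the move to patients. It cannot: conditions A and B in section (e) use primary diagnosis only. The consequence is confined to interpreting the treatment results, which makes this a worthwhile and cheap improvement and not a flaw that stops the study.

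**What to change.** Before the first scored encounter, amend section (d) so that:

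- the investigators who set the gold standard record, for each scenario and severity including the control, whether the standard is at drug or class level, and which medications and psychiatric treatments they accept as equivalent to the primary one;
- items 16 and 17 count a recommendation as correct if it includes any member of that set, with the single-item match reported beside it;
- the same maximum number of listed items is scored for Liv and for the psychiatrists. Without this limit, a wider accepted set would make a long list still easier to pass;
- the control entry states how a case with no indicated medication is scored.

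Which items belong in each set is for the investigators to decide; none is proposed here.

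The cost is SAP wording and one short list per scenario and severity. The downside is that the list must be agreed in advance and the criterion is less strict, which is the reason for keeping the single-item result alongside. The change does not add a direct Liv-versus-psychiatrist comparison of treatment, which section (d) also lacks.
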